#### Duration anticipated to enroll all subjects:

This is a two year study. Based on historical volume of patients with similar inclusion criteria within PI [name]'s clinical practice, it is anticipated that the desired number of participants (n=25) will be enrolled within the first year. Should enrollment be lower than anticipated after Year 1, the enrollment period will be extended into Year 2.

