Official Study Title:

Flexible representation of speech in the supratemporal plane

NCT Number:

NCT05209386

Document:

Statistical Analysis Plan

Document Date:

July 15, 2020

STATISTICAL DESIGN AND POWER ANALYSIS

Statistical Design, Power and Analytic Approach. We will test neurosurgical patients (ages 15-25 years) undergoing evaluation and treatment who require chronic (>7 d) sEEG implantation and recording of the temporal lobe for seizure localization or brain mapping. One set of behavioral tasks, and corresponding electrophysiological measures, will allow us to address Aim 1. Another will address Aim 2. Patient permitting, our goal is to have the same patient complete all tasks. All participants will undergo neuropsychological tests and will have detailed history/demographic information as part of their clinical battery.

Power and Sample Size. Robust behavioral effects will allow examination of perceptual weights in neural representation. Using behavioral effect sizes from **Figure 2** pilot data to estimate the sample size required for a predicted power of 0.8 (two-tailed alpha at .05) yields a sample of N=25. This leaves open the issue of power for neural measures. Our pilot EEG data with the same task/stimuli revealed robust effects with N=23 (**Figure A**), reassuring that N=25 is a reliable target for EEG. The SNR advantages of sEEG versus EEG, and our sEEG pilot data in **Figure 3**, suggest that this sample size will be more than sufficient for sEEG measures, especially as they will be utilized in a within-patient/within-electrode experimental design.

Analyses. Specific pre-registered analyses will assess the hypotheses outlined in the Approach section of the proposal. Specifically, we will test the following hypotheses:

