(**H1**) broadly, the relative perceptual weight of VOT and F0, as measured behaviorally, will be reflected in cortical response, (**H2**) with modulation as a function of baseline perceptual weights, (**H3**) shifts experimentally invoked by a change in listening context by presenting speech in noise, (**H4**) and by introducing an 'accent' that shifts short-term input regularities across VOT and F0. In the latter case, our approach will allow us to test the specific directional hypothesis (**H5**) that F0 perceptual weights in the DBSL paradigm are both exaggerated by Canonical input regularities that cleanly convey a VOTxF0 correlation consistent with English and that F0 perceptual weights are down-weighted upon introduction of a regularity that violates the typical pattern of English (supported by scalp EEG pilot, **Figure A**). Our use of sEEG allows us to evaluate these hypotheses across the supratemporal plane thereby testing the strong, and falsifiable, hypothesis (**H6**) that adaptive plasticity effects are present in HG versus (**H7**) apparent only at higher levels of the cortical hierarchy. Our ability to test these hypotheses is complemented by sEEG electrode placement in cortical regions outside STP (see **Figure 3**) which will support secondary hypotheses and serve as control electrode sites.

The study design is justified our extensive behavioral research demonstrating the feasibility of the project rationale. On the electrophysiological side, our pilot data (**Figures A,3**) demonstrate the feasibility of recording robust sEEG and EEG signals responsive to the acoustic dimensions we manipulate. This will provide clear, informative, interpretable data with which to evaluate the hypotheses listed above.

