High-gamma amplitude will be calculated using an approach that utilizes the Hilbert transform. Specifically, the signal will be filtered into 8 subbands, logarithmically spaced between 70-150 Hz. For each subband, we will calculate the amplitude (absolute value) of the analytic signal, which is estimated using the Hilbert transform. Each subband will be normalized to its baseline mean and standard deviation, estimated across trials. The HGA estimate is then the mean across these subbands.

We will use *least-squares linear regression neural encoding models* to investigate relationships between acoustic stimulus dimensions and STP neural responses during the baseline quiet context, in which stimuli sample a 2-d F0 x VOT grid. This approach will allow us to identify the subset of electrodes and temporal windows that encode at least one of these 2 dimensions at baseline; targeted analysis on this subset (described below) will then be used to compare listening contexts.

Encoding model inputs will consist of F0 and VOT, with an output of channel- and time-specific HGA. For a given electrode, individual models will be built using single trial data and a sliding window, allowing us to identify the temporal window relative to stimulus onset that yields significant models. Model quality will be assessed in two ways. First, using models built on all trials, we will calculate the regression *F*-statistic, which determines if any coefficients are significant. This will be compared to null distributions estimated with permutation tests that shuffle data across trials. Second, goodness-of-fit will be assessed for significant models by performing leave-one-out cross-validation and calculating R^2 , the proportion of variance in neural activity explained by the model. Finally, we will assess the relative encoding strength of each acoustic dimension using model coefficient *t*-statistics. In summary, this approach will allow us to identify the timing and anatomical location of F0 and VOT encoding during baseline quiet listening conditions for which dimensions are sampled orthogonally (as in **Figure 1a**).

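### No analysis stated in the SAP joins a patient's behavioural perceptual weight to a neural measure, so H2 has no direct test and H1 only an indirect one

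*SAP*

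**What the plan says.** The hypotheses are in the SAP, Analyses. H1 holds that the relative weight of VOT and F0, "as measured behaviorally, will be reflected in cortical response"; H2 continues "with modulation as a function of baseline perceptual weights". H3 to H5 are the specific forms: shifts under noise and under an artificial accent.

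Under Behavioral Analyses, the SAP computes one relative-weight index per patient, in quiet and in noise, from absolute correlations scaled to sum to one. Classification responses are modelled on VOT and F0, and for the accent blocks on block, F0 and their interaction, with patient as a random effect.

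Under Neural Analyses, "Encoding model inputs will consist of F0 and VOT" and the output is high-gamma activity (HGA) by channel and time. Noise is handled by comparing coefficient t-statistics across contexts. The accent contexts are handled by a cluster permutation test that shuffles context labels over single trials. The text predicts that HGA differences will follow behavioural weights, but attaches no statistic to that prediction.

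Under Power and Sample Size, pilot behavioural effects are used to "estimate the sample size required for a predicted power of 0.8 (two-tailed alpha at .05"), which "yields a sample of N=25". The SAP then acknowledges that power for neural measures is still open. It argues from EEG and sEEG pilot data, signal-to-noise ratio and the within-patient, within-electrode design that this number "will be more than sufficient for sEEG measures".

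**The concern.** A claim that neural encoding follows a listener's perceptual weights needs both quantities in one analysis. If they stay in separate models, the study yields two sets of results side by side, and the reader has to infer the link from their agreement in direction.

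That agreement is weak evidence, because the manipulations do more than move the weights. Noise alters the acoustic signal. The accent blocks alter the surrounding stimulus statistics. Either could change HGA for reasons that have nothing to do with how much a given patient relies on F0. Suppose F0 weight and neural F0 encoding both rise in noise in most patients, but the sizes of the two changes are unrelated across patients. Every planned contrast would come out as predicted, and nothing in the plan would show the missing association.

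The power argument raises a second, smaller matter. Its main strength is the within-patient, within-electrode design. With one baseline weight per patient, the natural test of H2 is across patients, where extra trials and electrodes sharpen each patient's estimate but do not add independent weights.

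**Working it through.** **Step 1: what each stated analysis contains** (SAP, Behavioral Analyses and Neural Analyses).

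| Analysis | Outcome | Predictors or comparison | Behavioural weight and neural measure together? |
|---|---|---|---|
| Mixed logistic model | classification | VOT, F0, patient | no (no neural term) |
| Accent mixed logit | classification | block, F0, block x F0, patient | no (no neural term) |
| Encoding model | HGA | F0, VOT | no (no behavioural term) |
| Noise comparison | encoding t-statistics | Baseline against Noise | no (no behavioural term) |
| Cluster test | HGA to Test stimuli | context labels | no (no behavioural term) |

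The covariate named in Rigor and Reproducibility is sex, which does not change the table. The weight index is computed for each patient and then used in none of these rows.

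**Step 2: the plan's own figure.** N=25 cannot be reproduced, because the pilot effect size is in a figure not shown in the copy reviewed. That is no fault of the plan. Back-solving for a paired contrast (two-sided 0.05, 80% power), the normal approximation gives (1.960 + 0.842)/sqrt(25) = 0.56, and the noncentral t gives 0.58. So N=25 is consistent with a standardized paired behavioural effect of about 0.56 to 0.58. That says nothing about a brain-behaviour association.

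**Step 3: a guide for a between-patient association.** Inputs: N=25 (SAP, and the same number in the protocol: "the desired number of participants (n=25) will be enrolled within the first year"); alpha 0.05 two-sided and power 0.80, borrowed from the behavioural calculation. Treating the link as one simple correlation is an assumption made here.

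Detectable r = tanh[(1.960 + 0.842)/sqrt(N - 3)]

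- N=25: tanh(2.802/4.690) = tanh(0.597) = 0.535
- N=20: tanh(2.802/4.123) = tanh(0.680) = 0.59
- N=15: tanh(2.802/3.464) = tanh(0.809) = 0.67

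The values 20 and 15 are assumed. The documents give no rate of unusable data, but completion of all tasks by each patient is only a goal, and enrolment equals the required sample with no allowance.

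Checks at N=25: a bias-corrected Fisher formula gives 0.528. Simulation from a bivariate normal (100,000 runs per value) gives power 0.79 at r=0.52 and 0.81 at r=0.53. Partialling out sex gives 0.545. A one-sided test gives 0.486, and treating the weight as a fixed predictor gives 0.505.

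**Step 4: power for smaller associations at N=25.**

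| True r | Power, Fisher z | Power, simulated | N for 80% power (Fisher z) |
|---|---|---|---|
| 0.3 | 0.31 | 0.31 | 85 |
| 0.4 | 0.51 | 0.52 | 47 |
| 0.5 | 0.73 | 0.75 | 30 |

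**The case against.** The strongest reply is that H1 is framed broadly and that H3 to H5 are how it is meant to be examined. The context manipulations are chosen because they move behavioural weights, and the SAP derives directional neural predictions from those expected moves. It also compares the relative encoding strength of F0 and VOT, which is a neural counterpart of the behavioural index. This stands: H1 does have indirect tests, and a reader who inferred that H1 and H2 are both wholly untested would go too far. The reply does not reach H2, and it does not separate an effect of weights from an effect of the changed stimuli or context.

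Second, a reader might set the figure of r about 0.54 against the sufficiency statement as a rebuttal. The SAP does not support that. It makes the statement for sEEG measures, leaning on within-patient and within-electrode contrasts, and never claims it for a between-patient correlation. Nor does the figure describe H1, which could be tested within patients, or the mixed model proposed below. It is also two-sided, whereas the SAP calls its neural predictions directional.

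Third, the between-patient reading of H2 is not certain. Baseline is also the SAP's name for the clear-speech context, so H2 could concern F0 against VOT within that context. One index per patient makes the between-patient reading the more natural one, but the SAP should say which is meant.

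Fourth, the SAP contains no rule that H1 or H2 will be accepted when group results move together. The risk is that the plan leaves this inference open, not that it prescribes it.

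Finally, the SAP points to pre-registered analyses and to an Approach section that were not supplied. A linking test may exist there. The finding is therefore limited to this SAP, which should state the test if there is one.

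**Conclusion.** The point holds in a limited form. As supplied, the SAP states no analysis containing both a patient's perceptual weight and a neural measure. H2 has no direct test. H1 is tested only indirectly, through separate behavioural and neural contrasts whose agreement would not show that encoding follows a patient's weights. This rests on the text alone and needs no numerical assumption.

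On precision, the supportable statement is that no power was computed for a between-patient association and that the sufficiency argument does not extend to one. The guide value of r about 0.53 to 0.54 at N=25 assumes a simple correlation, two-sided 0.05, 80% power and all 25 patients usable. It bears on H2 under its between-patient reading only. The change should be made, since the data needed for a direct test are already to be collected.

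**What to change.** **Neural Analyses: add one linking model.** Regress single-trial Baseline HGA, in baseline-significant supratemporal-plane channels and windows, on F0, VOT, the patient's baseline relative F0 weight, the interactions of that weight with F0 and with VOT, and sex. Enter only the F0 weight, because the index sums to one and the VOT weight is one minus it. Use random slopes by patient and by electrode within patient, and take the null from shuffling weights among patients.

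**Noise (H3).** Relate each patient's change in neural F0 encoding, Baseline to Noise, to the change in that patient's F0 weight index.

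**Accent (H4, H5).** The weight index is defined only in quiet and in noise, so use a patient-specific block x F0 slope from the mixed logit as the behavioural measure. The SAP lists that interaction as a fixed effect, so the model needs a by-patient slope for it. Like the H3 analysis, this rests on at most 25 patients.

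**If no linking model is added,** label H1 and H2 descriptive.

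**Power and Sample Size.** Say that the sufficiency statement concerns within-patient and within-electrode contrasts, and that no power was computed for a between-patient association. Give the correlation of about 0.53 to 0.54 as a guide, with its assumptions, and not as the power of the mixed model.

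**Cost.** SAP wording, one added analysis with its two extensions to the context shifts, and no new data. The downside is a less favourable statement about precision for H2.

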Evaluating the Hypotheses: Behavioral Analyses. We will evaluate the behavioral impact of the VOT and F0 acoustic dimensions on classification using *mixed-effects logistic regression* (with patient as a random effect, stimulus VOT and F0 as fixed effects and classification responses as the outcome). Following our prior work,^{14,25-29} perceptual weights for the dimensions will be computed for each patient as the correlation between dimension values and the proportion of *peach* classifications across all stimuli in the VOTxF0 stimulus grid with absolute values of the correlation coefficients normalized to sum to one as an *index of relative perceptual weight* in quiet (Aim 1) and in noise (Aim 2). To examine the impact of a change in 'accent' in the DBSL paradigm, we will use mixed logit models with responses as a function of patient, block, test stimulus F0 and the interaction between block and F0 (Aim 2). Patient will be modeled as a random effect, with the other factors as fixed effects.

Evaluating the Hypotheses: Neural Analyses. We will take a multi-pronged analysis approach. Our pilot data in **Figure 3** demonstrate that *high-y* activity (HGA) is modulated by graded acoustic details across the VOT and F0 dimensions across electrodes placed in the STP. Following the analysis pipeline used in our pilot data analyses, we will specifically examine stimulus-time-locked HGA to the *Test* stimuli, which possess consistent, perceptually-ambiguous VOT and differentiated F0. We have specific, directional predictions (detailed above)

regarding how HGA to F0-differentiated *Test* stimuli will vary according to perceptual weight in behavior. To briefly recap, we expect that HGA to *Test* stimuli will be better differentiated (1) in the Speech-in-Noise compared to the Clear baseline context (because F0 carries greater perceptual weight); (2) in the Canonical, compared to the Reverse, context; (3) in the Canonical, compared to the Baseline Clear Speech context (because stimulus statistics exaggerate the dimension regularity in behavior).

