To characterize shifts in neural encoding across listening contexts, we will investigate Noise using encoding models and Canonical/Reverse contexts using *cluster-based approaches*.^{32,49} Encoding models will be built from the Noise context for all channels and timepoints, using the same approach as Baseline. If a channel/timepoint is significant in either Baseline or Noise, the F0 and VOT coefficient *t*-statistics will be compared across contexts. We hypothesize that encoding of F0 will strengthen and VOT will weaken in Noise, as measured by changes in *t*-statistic magnitudes across multiple models. Next, we will compare neural responses for each of the two *Test* stimuli (which were embedded in the F0 x VOT grids, **Figure 1a**) between Baseline vs. Canonical and Canonical vs. Reverse. The clustering approach will look only at Baseline significant channels and time windows and involves randomly assigning listening context labels to single-trial data followed by a *t*-test at each time step. Across all permutations, a criterion value will be established for each timepoint (>95% of absolute value of *t*). For each of these permutations, we will next determine whether its value exceeds criterion across timepoints, and for how many timepoints it exceeds criterion (a 'cluster'). For each cluster, *t* values will be summed and assigned to all points in the cluster, with the largest summed cluster value stored for each permutation. This will create a null distribution of 1000 cluster values. We then will establish whether the cluster size calculated across real neural data (organized according to listening context) exceeds the 95% permutation-based cluster values such that $p < .001$ indicates an observed cluster is greater than all permutation-based clusters. Using this approach, we will identify context-dependent shifts in HGA responses, which we predict will reflect observed shifts in perceptual weights. Namely, we hypothesize that HGA responses in F0-encoding channels will be enhanced in the Canonical context relative to both Baseline and the Reverse context.

Rigor and Reproducibility. Analyses will be controlled for multiple comparisons, with sex as a co-variate in our analyses. We will use pre-registration and provide access to all the deidentified source data.

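### The only behavioural measure specified for both quiet and noise is a relative index, which scores a selective loss of VOT use as F0 up-weighting

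*SAP*

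**What the plan says.** All references are to the SAP.

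- *Evaluating the Hypotheses: Behavioral Analyses* first names a mixed-effects logistic regression, "with patient as a random effect, stimulus VOT and F0 as fixed effects and classification responses as the outcome". It lists no context term and no cue-by-context interaction.
- The same paragraph defines a per-patient relative-weight index from the correlations of VOT and F0 with the proportion of one response category over the stimulus grid, with "absolute values of the correlation coefficients normalized to sum to one". This is the only behavioural measure expressly assigned to both quiet (Aim 1) and noise (Aim 2).
- For the 'accent' manipulation it adds "mixed logit models with responses as a function of patient, block, test stimulus F0 and the interaction between block and F0". No equivalent is given for noise, and no test of the quiet-to-noise change in the index is stated.
- *Evaluating the Hypotheses: Neural Analyses* predicts that high-gamma responses to the Test stimuli, which have ambiguous VOT and differing F0, will separate better in noise than in clear speech, "because F0 carries greater perceptual weight". Later in the neural analyses, two effects are stated: "We hypothesize that encoding of F0 will strengthen and VOT will weaken in Noise". They are to be assessed with separate coefficient t-statistics.

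**The concern.** The index is a ratio, so it cannot tell whether F0 use went up or VOT use went down. Degraded VOT is a plausible effect of noise on its own. If that is all that happens, the index still reports a higher F0 weight.

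The reason given for the first neural prediction is a statement about F0. If the index is its only behavioural support, that reason may rest on a change that does not involve F0. The neural analysis also keeps F0 and VOT separate, so a single ratio has no counterpart for either neural effect. The plan specifies an interaction test for 'accent', which makes its absence for noise look like an omission.

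**Working it through.** **Inputs.** From the SAP: the index definition, an orthogonal VOT-by-F0 grid at baseline, N=25, and two-tailed alpha of .05. The available text gives no index value, grid size, trials per cell or cue slopes, so there is no figure of the plan's own to reproduce on this point. Assumed: a 5x5 grid with each cue coded -1 to +1, 10 trials per cell, and a logistic listener.

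**Formulas.**

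- p = 1/(1 + exp(-(bVOT·VOT + bF0·F0)))
- F0 index w = rF0/(rF0 + rVOT), using absolute correlations of each cue with p over the grid
- F0 effect at ambiguous VOT = p(VOT=0, F0=+1) - p(VOT=0, F0=-1). For bF0 = 1 this is 0.731 - 0.269 = 0.462, whatever bVOT is.

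**Step 1: loss of VOT use, expected values.**

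| bVOT | bF0 | rVOT | rF0 | w | F0 effect at ambiguous VOT |
|---|---|---|---|---|---|
| 4 | 1 | 0.957 | 0.179 | 0.158 | 0.462 |
| 3 | 1 | 0.948 | 0.255 | 0.212 | 0.462 |
| 2 | 1 | 0.903 | 0.405 | 0.310 | 0.462 |
| 1 | 1 | 0.705 | 0.705 | 0.500 | 0.462 |
| 2 | 0.7 | 0.949 | 0.292 | 0.235 | 0.336 |

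For example, 0.179/(0.179 + 0.957) = 0.158 and 0.405/(0.405 + 0.903) = 0.310. In the last row F0 use has fallen, yet the index is above its quiet value of 0.158. A 7x7 grid gives 0.161 and 0.312 for VOT slopes 4 and 2.

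**Step 2: where the rise comes from.** Letting only rVOT fall from 0.957 to 0.903, with rF0 held at 0.179, gives 0.179/(0.179 + 0.903) = 0.165. That is 0.007 of the total rise of 0.152. The rest comes from rF0, which grows because VOT drives less of the variation in responses and saturates fewer cells. Dropping the sum-to-one step alone would therefore not help.

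The same happens with the F0 effect fixed on the probability scale. With a linear listener, F0 at 0.10 per unit and VOT falling from 0.35 to 0.15:

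- w goes from 0.10/0.45 = 0.222 to 0.10/0.25 = 0.400
- rF0 goes from 0.275 to 0.555

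**Step 3: simulated studies.** Each has 25 patients, with mean VOT slope 4 (SD 0.5) and F0 slope 1 (SD 0.4), and a paired t-test on noise minus quiet:

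- VOT slope cut 25%, F0 unchanged: significant F0 increase in 97-98% with the index, and in 3% or fewer with per-patient logistic F0 slopes.
- VOT slope cut 50%, F0 unchanged: 100% against about 2%. Raw rF0 without normalisation also gives 100%.
- VOT slope cut 50%, F0 slope cut 30%: the index shows an increase in over 99%; the logistic slope shows a decrease in about 95%.
- VOT slope cut 50%, F0 slope raised 50%: both detect the increase in 100%.

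**Step 4: guessing.** If a fraction g of responses is random, expected proportions become g/2 + (1 - g)p. This is a linear rescaling, so both correlations and w are unchanged (0.158 at guess rates from 0 to 0.95). With binomial sampling, w is 0.157, 0.154, 0.158, 0.176 and 0.269 at guess rates 0, 0.2, 0.4, 0.6 and 0.8. Significant F0 increases occur in about 3%, 4-6%, 17% and 87% of studies at 0.2, 0.4, 0.6 and 0.8. The drift starts sooner with a weak F0 effect (slope 0.5: 0.085 at no guessing, 0.107 at 0.4, 0.143 at 0.6) or few trials (0.208 at 0.6 with 5 per cell).

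A logistic slope without a lapse term errs the other way. With no change in cue use, the F0 slope falls significantly in 52-58% of studies at 5% guessing, across simulation runs, and in 100% at 20%.

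**The case against.** The best defence is that the index does what its name says. H1 is about relative weight ("the relative perceptual weight of VOT and F0, as measured behaviorally, will be reflected in cortical response"), H3 speaks only of shifts, and the SAP labels the index as relative. For those hypotheses it is a fair measure. That stands.

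It is also true that 'F0 unchanged' depends on scale. When the VOT slope goes from 4 to 2, the grid-averaged effect of F0 on the response proportion rises from 0.099 to 0.167 per unit, so choices over the whole grid do depend more on F0. But the neural prediction concerns ambiguous-VOT stimuli, where the F0 effect is the same, and the linear example shows the index rising with the probability-scale effect held fixed.

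The logistic model could be fitted in each context without contradicting the text, and the SAP refers to pre-registered analyses that are not in these documents. So the accurate statement is that no cue-by-context test for noise is written here, not that none could be done. The neural F0 and VOT effects have their own t-statistics, and the index does not decide them.

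A reader might go further in three ways that the documents do not support:

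- That the sum-to-one step forces the F0 weight up whenever rVOT falls. The ratio rises only if rF0 does not fall in proportion, and Step 2 shows that normalisation contributes little here.
- That guessing in noise would confirm F0 up-weighting in almost any case. Step 4 shows that it does so mainly at high guess rates, with few trials or with a weak F0 effect. Guessing also shrinks F0's own effect, and the documents give no noise level or guess rate.
- That H3 itself claims F0 strengthening and VOT weakening separately. That two-part claim appears only for the neural encoding models.

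**Conclusion.** The concern holds in limited form. As written, the only behavioural quantity expressly specified in both quiet and noise is a relative index. A selective loss of VOT use raises it when F0's logit effect, and its effect at ambiguous VOT, is unchanged or falls. Under the assumed values the index about doubles (0.158 to 0.310) when the VOT slope is halved, and at N=25 the change would almost always be significant.

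The index can describe relative weight. It cannot by itself support the statement that F0 carries greater weight in noise, nor be matched one-to-one with the separate neural F0 and VOT effects. The direction of the effect follows from the definition. Its size depends on assumed slopes, patient spread, grid and trial counts, and should be recalculated with the study's own values.

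**What to change.** Fit one mixed-effects logistic model to the quiet and noise grid trials together, with context, VOT, F0, VOT-by-context and F0-by-context terms and by-patient random slopes. Include a context-specific lapse (guess-rate) term, because without one even modest guessing in noise would look like F0 down-weighting.

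Base any claim of F0 up-weighting on F0-by-context and any claim of VOT down-weighting on VOT-by-context. Report the index beside them, described as relative weight only.

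This uses trials already planned and needs only a change to the SAP. The costs are a slightly more complex model, since the lapse term goes beyond a standard mixed logit, and a claim of F0 up-weighting that is harder to make. In Step 3, separate slopes still detected a true 50% rise in the F0 slope in every simulated study.

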All auditory stimuli will be adjusted to a comfortable level for each participant as determined by a calibration process completed by the participant. The blocks can be completed with breaks in between as needed or desired and can occur over the course of the participant's clinical stay in the EMU. All blocks involves listening to sound via earphones and making a categorical decision. Because participation is self-paced, the number of sessions in a day over the total course of an individual's participation will depend on their schedule, health, and motivation to complete research tasks. This period may be up to 10 days, however the patient participant's inpatient stay will not be extended for research purposes.

sEEG electrodes and scalp EEG electrodes will be connected to the study team's recording system before beginning research tasks in order to collect neural recordings specifically for research. The recording system will be disconnected at the completion of each research session. sEEG electrodes will be connected to the EMU's recording system for the duration of each participant's inpatient stay per standard of care.

The study team's recording equipment consists of the software required to present stimuli on MATLAB and record electrical signals from electrodes as well as behavioral responses from subjects. Therefore, no audio or visual recordings will be taken.

The risks and benefits of clinical procedures that are part of the patient's standard of care will be explained in a consent process separate from research activities. Electrode placement and recording are conducted strictly based on a patient's clinical needs and will not be dictated or manipulated by research. Participants will incur minimal additional risk by participating in the behavioral research task. Any risks involved will be explained and documented in the informed consent process and may include fatigue, boredom, or frustration. Research staff will ensure that participants and parents/guardians are aware that participation is entirely voluntary and may stop at any time. Every effort will be made to ensure patient comfort throughout study procedures.

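### Both behavioural mixed logit models name patient as the only random effect; if the block-by-F0 effect varies between patients, the nominal 5% accent test is too liberal (about 6-39% over assumed ranges)

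*SAP*

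**What the plan says.** The SAP, under Evaluating the Hypotheses: Behavioral Analyses, describes two mixed logistic models.

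- **VOT/F0 classification model:** it is to be fitted "with patient as a random effect, stimulus VOT and F0 as fixed effects and classification responses as the outcome".
- **Accent (DBSL) model:** it takes "responses as a function of patient, block, test stimulus F0 and the interaction between block and F0", and the allocation of terms is then given as: "Patient will be modeled as a random effect, with the other factors as fixed effects".

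In the same paragraph, "perceptual weights for the dimensions will be computed for each patient", so the SAP treats VOT and F0 weights as patient-level quantities. H2 also expects modulation by baseline weights.

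The Rigor and Reproducibility paragraph adds a general rule: "Analyses will be controlled for multiple comparisons, with sex as a co-variate in our analyses". It says nothing about variance between patients. The Power and Sample Size paragraph gives N=25, power 0.8 and "two-tailed alpha at .05". No between-patient SD of the accent effect and no number of test trials is stated. The SAP refers to a pre-registration, which is not among the documents.

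**The concern.** A patient intercept absorbs differences in overall response bias. It does not absorb differences in how far a patient's use of F0 shifts between blocks. If that shift varies and the model has no term for it, the standard error of the average shift reflects trial noise only. Trials, rather than patients, then set the apparent precision.

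The block-by-F0 term is the SAP's behavioural test of the accent effect. It bears most directly on H5, which is stated in terms of F0 weights in this paradigm; H4 is worded mainly about cortical response. With the component omitted, the interval is too narrow, and a shift carried by a few patients could be reported as general. The F0 and VOT tests in the first model are exposed in the same way to variation in those slopes.

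**Working it through.** **The plan's own figure.** N=25 is derived from pilot effect sizes in a figure that is not shown. For a two-sided paired t-test at 5% and 80% power, N=25 corresponds to a standardised effect of 0.584. Without the pilot value, N=25 can be neither confirmed nor refuted.

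**Inputs.** From the documents: 25 patients, two-sided 5%, repeated trials per patient in every block, and the model terms above. Assumed: two block levels (Canonical, Reverse) and two F0 test stimuli; m = 10, 20 or 40 trials per cell; between-patient SD of block-by-F0 (tau) of 0 to 1.5 logits; true average interaction zero.

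**Hand check.** A cell's logit has sampling variance of about 1/(m p(1-p)), so a four-cell interaction contrast has 4/(m p(1-p)). Varying effects add tau² per patient. The ratio of true to modelled variance is therefore

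1 + tau² m p(1-p)/4.

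With tau = 1, m = 20 and p = 0.5, this is 1 + 20 × 0.25/4 = 2.25. The test behaves as if its critical value were 1.96/√2.25 = 1.31, a two-sided error of 19%. The number of patients cancels, so recruiting more does not help; more trials per patient make it worse.

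**Simulation.** Data were generated with intercept SD 0.5, average F0 effect 1.5 logits (SD 0.5) and block SD 0.3. The random-intercept model was fitted by Laplace approximation to 3,000 data sets per scenario. Rejection rates of the nominal 5% Wald test:

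| Trials per cell | tau 0 | tau 0.5 | tau 1.0 | tau 1.5 |
|---|---|---|---|---|
| 10 | 5% | 6% | 10% | 17% |
| 20 | 5% | 8% | 16% | 27% |
| 40 | 5% | 11% | 26% | 39% |

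A separate simulation used 21-point Gauss-Hermite quadrature, intercept SD 0.7 and no F0 or block variation. Over the same four SDs it gave 5.2 / 6.5 / 11.4 / 17.1% at 10 trials, 5.1 / 8.6 / 17.0 / 26.7% at 20, and 5.4 / 11.5 / 26.8 / 38.9% at 40. Monte Carlo error is about 0.4 points at 5% and 0.9 points at 39%.

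**What drives it.**
- F0-slope variation alone does not inflate the test, because it cancels in the within-patient difference between blocks: 4.6% (F0-slope SD 0.75, 20 trials) and 4.3% (SD 1.5, 40 trials).
- At tau 1.0 and 20 trials, the mean reported SE is 0.194 against 0.284 from per-patient contrasts. The interval has 0.194/0.284 = 68% of the width it should have.
- In that setting the rate is 15% with 15 patients, 16% with 50, and 17% if trials per cell range from 5 to 35 across patients.
- A likelihood-ratio test does no better: 15% (tau 1.0, 20 trials) and 40% (tau 1.5, 40 trials).

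**Alternatives.** A one-sample t-test on per-patient contrasts stayed at 4.1-5.7% in the first simulation and 4.4-6.0% in the second. A by-patient slope model (1,500 data sets per scenario, one run) gave 6.1-6.7% with a Wald z at tau of 1.0 or more. With a t reference on 24 df it gave 3.6-5.3% over all scenarios tried.

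**First model.** Assuming a 5 × 5 grid and an average F0 slope of zero, the F0 test rejected 8% / 23% at F0-slope SD 0.5 / 1.0 with 4 repeats per stimulus, and 16% / 37% with 10 repeats (6% at SD 0). A smaller repeat run of 400 data sets per scenario gave 9.5 / 22% and 16.5 / 40%.

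**The case against.** The strongest reply is that the SAP is underspecified rather than wrong. It never uses the word intercept, a model with by-patient slopes also has block, F0 and block-by-F0 as fixed effects, and the unseen pre-registration may settle the matter. That stands as a reason for caution. Still, the sentence places only patient in the random part, and an analyst following it would fit the intercept model.

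Second, the size rests on assumed inputs. The 39% corner needs tau = 1.5, 40 trials per cell and a zero average. About half of patients would then shift by more than 1 logit, in directions that cancel, whereas H5 predicts one direction. This is fair: at tau 0.5 the rate is 6-11%, and if the effect is real the practical harm is an interval that is too narrow rather than a false positive. For the same reason the first-model figures matter less, since a zero average F0 effect is of little interest here.

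Third, the levels of block are not stated. If Baseline is a third level, the test has 2 df and the table does not describe it. The problem remains, however: the 2-df test rejected about 22% at tau 1.0.

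Fourth, the Protocol's remark that "participation will depend on their schedule, health, and motivation to complete research tasks" concerns sessions per day and is only weak evidence of unequal trial counts. Unequal counts barely change the result in any case.

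Finally, the consequence is confined to behaviour. Electrode selection, the neural permutation tests and the per-patient weight index do not use these p-values.

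**Conclusion.** The concern holds, conditionally. As written, the accent model omits between-patient variation in the block-by-F0 effect, and nothing else in the documents supplies it. If that effect varies, the nominal 5% test rejects in roughly 6-39% of null data sets over tau 0.5-1.5 and 10-40 trials per cell; with tau 1.0 and 20 trials the figure is about 16%. If it does not vary, the test is sound and the change is merely a cheap safeguard. Variation is plausible but not documented, so confidence in the size is medium. The sex covariate and multiplicity control do not address it. The plan should be corrected before the behavioural analysis is run.

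**What to change.** State the random-effects structure in the SAP: by-patient slopes for F0 and VOT in the first model, and for F0, block and block-by-F0 in the accent model. If the fit does not converge, drop the correlations first and keep the block-by-F0 slope.

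Base the block-by-F0 p-value and interval on a t-test of per-patient contrasts, or on the slope model with a t reference on patients minus 1 df, not on a Wald z. Sex can enter the patient-level test as a covariate. Report the estimated between-patient SD. Name the levels of block; if Baseline is one of them, define a per-patient contrast for each comparison H5 needs, under the SAP's multiplicity control. If the pre-registration already contains this structure, copy it in.

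This takes one or two sentences and no new data. The price is wider intervals, some convergence handling and less apparent power. With an assumed average interaction of 0.75 logits, tau 1.0 and 20 trials per cell (2,000 data sets), the patient-level test has 72% power. The random-intercept test shows 91%, but its type I error in that setting is 16%.
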